# 3. STUDY DESIGN

[Chart review of children and young people with Neuromuscular disease or with Cerebral Palsy who are cared for in the Royal Brompton Hospital and that have been treated with nebulised hypertonic saline for at least 12 months. Children and young people who are also diagnosed with Cystic Fibrosis will be excluded.

Parents or legal guardians will be asked to complete two questionnaires to further complement data from hospital records.

Participants between 10 and 18 years old will be asked to complete one questionnaire to complement hospital records.]

[Duration: 6 months.]

[We aim to review all charts of participants recruited that meet criteria between December 2011 and May 2018. We aim to recruit 40 participants from each group, including children, young people, and parents or legal guardians, as this will be a pilot study. Only participants recruited will have their charts reviewed]

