#### **ELIGIBILITY**

Inclusion cirteria: Children and young people with Neuromuscular disease or Cerebral Palsy who have their care at the Royal Brompton Hospital and are on treatment with nebulised Hypertonic Saline for at least 12 months.

Exclusion criteria: Children or young people also diagnosed with Cystic Fibrosis.

**DURATION** 6 months

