Children with Neuromuscular disease show a decline of Forced Vital Capacity (FVC), which is steeper at younger ages (13). This is especially important because the age at which FVC reaches 1 Lt and the rate of decline of FVC are variables that can predict mortality (14).

Pneumonia, respiratory exacerbations and failure are one of the most important causes of emergency admissions, hospitalisations and death in children with neuromuscular diseases and cerebral palsy (15-18). Physical health and the number of days spent outside home or hospitalised are important domains of life and predictor of Health-Related Quality of Life in children with Neuromuscular disease and children with Cerebral Palsy (19,20). In this context, it is of importance to research how to therapeutically aid airway clearance, decrease respiratory exacerbations and reduce the pulmonary function rate of decline.

Hypertonic Saline is a solution of salt water used as a nebulized medication in many conditions. Its clinical benefits include mucus clearance, microbiological diagnosis, improvement of lung function, decrease in respiratory exacerbations, cough triggering and improvement of quality of life (21). It has mucolytic and expectorant effect, reduces biofilm formation by Pseudomonas Aeruginosa and increases antioxidative thiols in the airway liquid (22).

Retrospective studies and clinical trials have shown that inhaled Hypertonic Saline is well tolerated, reduces pulmonary exacerbations, improves lung function and Lung Clearance Index, reduces absenteeism, improves Health Related Quality of Life in patients with Cystic Fibrosis independent of rhDNase treatment (23-26), and has anti-inflammatory effect in sputum decreasing

IL-8 (27). In asthmatic and healthy subjects, inhaled Hypertonic Saline have shown to enhance mucociliary clearance (28). To date, studies investigating Hypertonic Saline in bronchiectasis have produced conflicting results (29).

This study aims to assess the effectiveness of the use of nebulised Hypertonic Saline in respiratory outcomes in children and young people with Neuromuscular disease or with Cerebral Palsy.

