#### 7.2 CONSENT

Consent to enter the study must be sought from each participant only after a full explanation has been given, an information leaflet offered, and time allowed for consideration. Signed participant consent should be obtained. The right of the participant to refuse to participate without giving reasons must be respected. After the participant has entered the study the clinician remains free to give alternative treatment to that specified in the protocol at any stage if he/she feels it is in the participant's best interest, but the reasons for doing so should be recorded. In these cases, the participants remain within the study for the purposes of follow-up and data analysis. All participants are free to withdraw at any time from the protocol treatment without giving reasons and without prejudicing further treatment.

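### Charts are read only for recruited families, so children who completed a year on saline and then died, left or declined drop out of both periods, with no count of how many or why

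*Combined protocol and SAP*

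**What the plan says.** Section 3 (Study Design) sets the look-back: "We aim to review all charts of participants recruited that meet criteria between December 2011 and May 2018". It gives "Duration: 6 months" for the study and adds that "Only participants recruited will have their charts reviewed".

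Section 7.2 (Consent) makes entry voluntary: "Signed participant consent should be obtained", and "The right of the participant to refuse to participate without giving reasons must be respected". The Eligibility entry of the Study Summary is in the present tense: children have their care at the hospital and "are on treatment with nebulised Hypertonic Saline for at least 12 months". Section 4.2 is looser, asking only for at least 12 months of treatment.

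Section 2 sets the comparison for antibiotic courses, respiratory hospitalisations and lung-function decline against the year before treatment. The lung-function objective covers only participants with neuromuscular disease who can perform spirometry. Section 3.1 does not list death among the endpoints. Section 6 plans no count of eligible children who were not recruited and no analysis of how they might differ.

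Section 1.1 (Background) states that "Pneumonia, respiratory exacerbations and failure are one of the most important causes of emergency admissions, hospitalisations and death" in these children. It also says that the age at which FVC falls to 1 litre and "the rate of decline of FVC are variables that can predict mortality".

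**The concern.** Whether a chart is read depends on what happened to the child after saline began: being alive, still under care and willing to consent, up to about 6.5 years later. The Background links both respiratory events and FVC decline to death, and these are also primary endpoints. Absence through death may therefore be tied to the outcomes being measured.

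There is no untreated comparison group. If the absent children had worsened after starting saline by more than the retained children did, removing them would look like a treatment effect. Separately, the primary objective concerns respiratory complications in general, yet the gravest of them cannot be counted. Without a denominator, a reader of the results could not tell whether 2% or 30% of eligible children were missing (figures for scale only).

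**Working it through.** **No figure in the plan to reproduce.** The 40 per group is justified only by pilot status. The documents give no number of eligible children, deaths or refusals, and no before/after correlation. The sizes below are illustrations on stated assumptions.

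**1. Who can enter.** Section 3 limits chart review to recruited participants. Section 7.2 makes recruitment depend on consent. The Study Summary requires current care and current treatment. Read together, these leave no route for a child who reached 12 months and then died, left or was not consented. No section names deceased children or says whether bereaved parents could be approached, so this is an inference from the three texts.

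**2. Which comparison is affected.** The same children supply both years, so an absent child leaves both. The contrast is biased only if absence is related to the change, not merely to the level.

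**3. Slope of lung function.** Assume before- and after-slopes with SD 1 (higher is better) and correlation ρ, no treatment effect, and the fraction *f* with the steepest after-period decline never recruited.

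- Shift in the after-slope: s = φ(z_f)/(1 − f). For f = 0.10: 0.1755/0.90 = 0.195 SD.
- Shift in the before-slope: ρ × s.
- False improvement in the change: (1 − ρ) × s.

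| ρ | f = 5% (s = 0.109) | f = 10% (s = 0.195) | f = 20% (s = 0.350) |
|---|---|---|---|
| 0.3 | 0.08 | 0.14 | 0.25 |
| 0.5 | 0.05 | 0.10 | 0.18 |
| 0.7 | 0.03 | 0.06 | 0.11 |
| 0.9 | 0.01 | 0.02 | 0.04 |

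When absence depends only on a stable severity common to both years, simulation (2 million draws) gives a false improvement of 0. So at f = 10% the range is 0 to 0.14 SD.

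**4. Chance of a false finding.** For a paired comparison of 40 children, SE = √{[(1 − ρ)²V + 1 − ρ²]/40}, with V = 1 + z_f s − s². At ρ = 0.5 and f = 10%, V = 0.712 and SE = 0.152, so 0.097/0.152 = 0.64. The chance of a falsely significant benefit is 1 − Φ(1.96 − 0.64) = 9.3%, against a nominal 2.5%. At f = 5% and 20% it is 5.4% and 21.5%. Two limits apply: section 6 names an independent t test and Mann-Whitney for this endpoint rather than a paired test, and the spirometry subgroup may be smaller than 40.

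**5. Event rates.** Assume 3 events a year, log-rate SD 0.8, before/after correlation 0.3 to 0.6, Poisson counts, no treatment effect, and log-odds of absence rising by 1 to 2 per unit of log rate. The simulation used 400,000 children per setting.

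| Absent | Absence follows after-year rate | Absence follows before/after average or stable severity |
|---|---|---|
| 5% | 0.93 to 0.98 | 1.00 |
| 10% | 0.89 to 0.97 | 1.00 |
| 20% | 0.82 to 0.94 | 1.00 |

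The entries are apparent after/before rate ratios. The second column applies only if absence follows the after-year itself.

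**The case against.** The strongest reply is that the numbers depend on what drives absence. Each child's after-period is 12 months (the parents' questionnaire asks about that span), and the deaths in question come after it is complete. They may reflect underlying severity, present in both years, rather than a change between them; the before/after contrast is then unbiased. This stands, and it is why the ranges reach 1.00 and 0.

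Several stronger readings are tempting but not supported:

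- A reader might infer that children are missing from the after-period only. They are missing from both.
- A reader might take the 0.195 SD shift in the after-slope as the bias. The objective is the change, so the bias is (1 − ρ) times that.
- A reader might state as fact that the fastest decliners are the ones missing. The Background makes this plausible for deaths; it says nothing about refusals, which could equally remove children who are well.

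It can also be said that a deceased child falls outside a population defined by current care and treatment. That is a fair reading of the Study Summary, but it narrows the conclusion to survivors still on treatment, whereas the hypothesis in section 1.2 is about children with these conditions in general. Finally, this is an exploratory pilot with ethics approval and consent-based access. That argues against demanding individual charts without consent, but not against reporting a denominator.

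**Conclusion.** The gap is real: the plan compares before with after in a group selected on later survival, continued care and consent, with no eligible denominator and no deaths counted. Whether this biases the contrast, and by how much, cannot be settled from the documents. With no treatment effect and an assumed 10% absent, the rate ratio would lie between 0.89 and 1.00, and the false improvement in slope change between 0 and 0.14 SD. The slope figure concerns only participants with neuromuscular disease who can perform spirometry; the selection itself reaches every primary endpoint. The direction is towards benefit if absence follows worsening after saline began, absent if it follows stable severity, and unknown for refusals. In every case deaths go uncounted and generalisability is limited. This is a moderate point that should be addressed; it does not invalidate a pilot.

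**What to change.** **Section 3.** Have the existing care team produce non-identifiable aggregate counts of all children with neuromuscular disease or cerebral palsy who started nebulised hypertonic saline in the window. Separate those who reached 12 months from those who did not, and show recruited, declined, transferred, and died (respiratory / other), by disease group and age band. Report deaths descriptively for all starters. They cannot be compared before and after, since every child was alive when saline began.

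**Section 6.** Add a tipping-point analysis. Let *f* be the absent fraction among children who reached 12 months and D the mean improvement observed in those recruited. The overall mean change is (1 − f)D + f × D_absent, which is zero when the absent children worsened on average by D(1 − f)/f. At f = 10% this is 9 times D; for D = 0.0975 SD it is 0.88 SD. Report that amount for each primary endpoint expressed as a mean change. If it is clinically plausible, limit the conclusion to surviving, consenting children. Assigning the absent children no improvement would be too weak: at 10% absent, a ratio of 0.89 becomes about 0.9 × 0.89 + 0.1 × 1.00 = 0.90.

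**Cost.** Protocol and SAP wording, a small amount of log work and possibly a minor ethics amendment. The headline may look less favourable. No further child is approached and no care changes.

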#### 3.1 STUDY OUTCOME MEASURES

**Primary Endpoints:** 

- Number of respiratory exacerbations requiring antibiotic treatment.
- Number of hospitalsiations due to respiratory exacerbations, using NHANES 2011 questionnaire for Hospitalisation and access to care HUQ.010.
- Nocturnal oximetry and polygraphy outcomes: Basal SpO2 (%), Minimum SpO2 (%), Maximum SpO2 (%), Average SpO2 (%), Oxygen desaturation index (ODI), Snoring and End tidal CO2 (EtCO2).
- Rate of decline of pulmonary function.

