#### **OUTCOME MEASURES**

- 1) Number of respiratory exacerbations requiring antibiotic treatment.
- 2) Number of hospitalisations due to respiratory exacerbations, using NHANES 2011 questionnaire for Hospitalisation and access to care HUQ.010.
- 3) Nocturnal oximetry and polygraphy outcomes: BasalSpO2 (%), Minimum SpO2 (%), Maximum SpO2 (%), Average SpO2, Oxygen desaturation index (ODI), Snoring and End tidal CO2 (EtCO2).
- 4) Rate of decline of pulmonary function.
- 5) Score on the ease of airway clearance pictorial analogue scale from participants.
- 6) Participants' perception of treatment.

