#### 1.2 RATIONALE FOR CURRENT STUDY

[To our knowledge, there is currently no available data concerning the use of nebulised Hypertonic Saline in the management of children and young people with Neuromuscular Disease or with Cerebral Palsy. This study aims to assess whether the use of nebulised Hypertonic Saline in children and young people with Neuromuscular disease or Cerebral Palsy is effective in the management and prevention of respiratory-related complications.

Hypothesis: Nebulised Hypertonic Saline in children and young people with Neuromuscular disease or Cerebral Palsy decreases respiratory-related complications.]

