## Secondary Objectives:

- Assess the effect of the treatment with nebulised hypertonic saline in children and young people with Neuromuscular disease or Cerebral Palsy on the number of courses of antibiotic prescribed compared to year before starting treatment.
- Determine whether the use of nebulised Hypertonic Saline in children and young people with Neuromuscular Disease or Cerebral Palsy reduces the frequency of hospitalisations due to respiratory exacerbations compared to year before commencing treatment.
- Explore the impact of the treatment with hypertonic saline on nocturnal oxygenation and ventilation in children and young people with Neuromuscular disease or with Cerebral Palsy.
- Evaluate whether the treatment with nebulised hypertonic saline in children and young people with neuromuscular disease or cerebral palsy improves the ease of airway clearance.
- In the subgroup of participants with neuromuscular disease who can perform spirometry, assess whether the use of Hypertonic Saline decreases rate of decline of pulmonary function compared to year before commencing treatment.
- Explore how parents of children and young people with Neuromuscular disease or with Cerebral Palsy perceive the treatment with nebulised hypertonic saline compared to previous management.

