#### 4.2 INCLUSION CRITERIA

[Children and young people under 18 years old with Neuromuscular disease or with Cerebral Palsy treated with nebulised Hypertonic Saline for at least 12 months and their parents or legal guardians.]

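### No rule, and no masking to period, is described for deciding whether an admission or an antibiotic course was a respiratory exacerbation

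*Combined protocol and SAP*

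**What the plan says.** Section 3.1 gives the first primary endpoint as "Number of respiratory exacerbations requiring antibiotic treatment". The Study Summary gives the second as "Number of hospitalisations due to respiratory exacerbations", and both places add "using NHANES 2011 questionnaire for Hospitalisation and access to care HUQ.010". The hypothesis in Section 1.2 has a direction: "Nebulised Hypertonic Saline in children and young people with Neuromuscular disease or Cerebral Palsy decreases respiratory-related complications".

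The main source is the hospital chart. Section 3 states "Only participants recruited will have their charts reviewed", and parents fill in questionnaires "to further complement data from hospital records". Section 4.2 admits only children "treated with nebulised Hypertonic Saline for at least 12 months", so the start date of saline separates the two periods for everyone.

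The antibiotic variable is worded in more than one way. The secondary objective in Section 2 concerns the "number of courses of antibiotic prescribed compared to year before starting treatment", with no respiratory condition, and the analysis plan in Section 6 likewise refers only to courses. The admissions objective in Section 2 keeps the respiratory cause.

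No section defines a respiratory exacerbation, says who reads the charts, or describes an abstraction form, masking, duplicate reading or adjudication. The Assessment and Follow-up section is marked as not applicable.

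**The concern.** Counting events by cause calls for a judgement whenever the recorded reason is mixed or vague. Section 1.1 itself describes reflux, impaired swallowing, chronic aspiration and recurrent infection in these children, so some unclear episodes are plausible. Finding the two windows in a chart requires the start date of saline, so unless a step prevents it, whoever classifies an event can see which side of that date it lies on. With no written rule and a stated expected direction, doubtful events could be counted more readily before saline than after. That would create or enlarge an apparent benefit, and a significance test on the resulting counts could not tell it from a real one.

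**Working it through.** **1. Which endpoints need attribution**

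| Place | Antibiotics | Admissions |
|---|---|---|
| Study Summary and Section 3.1 | respiratory exacerbations treated with antibiotics | due to respiratory exacerbations |
| Section 2, secondary objectives | courses prescribed, no cause stated | due to respiratory exacerbations |
| Section 6, analysis plan | courses, no cause stated | number only, no cause stated |

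For admissions, endpoint and objective agree on respiratory cause, and only the short label in Section 6 omits it. For antibiotics, Section 3.1 needs attribution, while Sections 2 and 6 as worded do not.

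**2. Size of the possible bias**

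The documents give no event rates and no share of doubtful events, so every input here is an assumption. Let *q* be the share of candidate events that are doubtful, and *b* and *a* the probabilities of counting a doubtful event before and after saline. Clear events are always counted, and there is no true effect:

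apparent rate ratio = [(1 − q) + q·a] / [(1 − q) + q·b]

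With b = 0.8:

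| q | a = 0.7 | a = 0.6 |
|---|---|---|
| 0.2 | 0.94/0.96 = 0.98 | 0.92/0.96 = 0.96 |
| 0.3 | 0.91/0.94 = 0.97 | 0.88/0.94 = 0.94 |
| 0.4 | 0.88/0.92 = 0.96 | 0.84/0.92 = 0.91 |

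The direction is also assumed. Exchanging *a* and *b* gives the reciprocals, about 1.02 to 1.10.

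**3. Effect on a test**

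Section 6 aims for 40 participants per group, justified only as a pilot. No alpha, power, effect size or rate is given, so that figure cannot be reproduced; it serves here only as 40 child pairs. Counts were simulated with no true effect, 2 or 4 candidate events per child-year, with and without variation between children (Poisson and gamma-Poisson), 4000 runs each. The test was a two-sided 5% paired t-test, a stand-in for a within-child comparison and not the chi-square test that the plan names.

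| b, a | Ratio at q = 0.1, 0.2, 0.3 | Rejection rate over all q and settings |
|---|---|---|
| 0.5, 0.5 (no bias) | 1.00, 1.00, 1.00 | 4.1% to 5.6% |
| 0.6, 0.4 | 0.98, 0.96, 0.93 | about 5% to 9% |
| 0.7, 0.3 | 0.96, 0.92, 0.87 | about 5% to 20% |
| 1, 0 (extreme) | 0.90, 0.80, 0.70 | about 9% to 80% |

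The effect is small when few events are doubtful, and large only when many are and the classification is strongly one-sided.

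**4. What removes it**

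If a = b, the formula gives 1.00 for every *q*. Masking the period aims at that equality. An all-cause count reaches it directly, because every event is counted (a = b = 1).

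**The case against.** The strongest reply is that the case rests on silence. The documents do not say who abstracts, what that person knows, or whether cause is re-judged or simply copied from the record. That stands. A reader might infer that an unmasked team is sorting events in favour of saline, but the documents support only that no rule and no masking are described.

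A second reply is that charts are not the only source. The admissions endpoint cites a questionnaire item, and the appended parent questionnaire asks for oral and intravenous courses in the 12 months before and after saline. This also stands, and it limits the remedy: parents know the period, so masking cannot reach their counts.

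Third, if the analysis simply counts courses, the antibiotic endpoint needs little judgement. That is correct on the wording of Sections 2 and 6, but it conflicts with Section 3.1, and the admissions endpoint would still be exposed.

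Fourth, the study is a pilot with an exploratory primary objective, and the illustrated bias is modest. Both are true and lower the priority. They do not remove the point, since Section 1.2 aims to assess whether the treatment is effective and Section 9 intends publication.

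**Conclusion.** The point holds as a gap in outcome ascertainment that should be closed cheaply; it is not a fatal flaw. An attribution step is required, no rule or masking is described, and the period is recoverable from the chart. The size cannot be derived from the documents. On the assumptions in the first ratio table, the spurious rate ratio is about 0.91 to 0.98, in addition to any other before/after bias.

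Three stronger readings are tempting and not supported. Bias is not shown to have occurred. Attribution is not shown to govern both endpoints: admissions need it under Sections 2 and 3.1, whereas antibiotics need it only if Section 3.1 prevails. Nor is the problem beyond repair at analysis, because all-cause counts need no attribution, although they answer a broader question and may dilute a true respiratory effect.

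**What to change.** First, reconcile Sections 2, 3.1 and 6 on whether the antibiotic endpoint is exacerbations or courses, and give the admissions variable in Section 6 its cause. Then:

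1. Log every antibiotic course and admission in both 12-month windows, with its date and verbatim reason, and lock the log.
2. Fix a written rule for what counts as respiratory before classifying. Classify from shuffled reason text with date, child ID and any mention of saline hidden, allowing a doubtful category. Assign the period afterwards by program, from a separately stored start date.
3. Report all-cause courses and admissions as a sensitivity analysis, and the respiratory counts with doubtful events included and excluded.
4. Make chart-derived counts primary and report questionnaire counts separately, since parents cannot be masked to period.

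The cost is a somewhat longer abstraction with no extra staff. The added time depends on the number of events, which the documents do not give. Masking will be imperfect if the same person logs and classifies, because some reasons may be recognised; a different person for step 2 would help where one is available.

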# Statistical Analysis Plan:

Primary endpoint analysis:

- Univariate X analysis for categorical variables to investigate *Courses of antibiotic treatment*.
- Univariate X analysis for categorical variables to investigate *Number of hospitalisations*.
- Student t testing will be used to analyse *nocturnal oxygenation and ventilation outcomes* comparing one year before and after starting treatment with Hypertonic Saline.
- Independent t testing and Mann-Whitney U test to analyse *Rate of decline in pulmonary function*.
- Cox proportional hazard model to test differences in primary endpoints *for different baseline*

Secondary enpoint analysis:

- Univarate analysis to analyse *Ease of airway clearance*.
- Univariate analysis on **perception of treatment**.

Data and all appropriate documentation will be stored for a minimum of 10 years after the completion of the study, including the follow-up period.

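### Ten variables are labelled primary with none chosen to decide the hypothesis, and section 2 lists the same outcome families as secondary objectives

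*Combined protocol and SAP*

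**What the plan says.** Section 3.1 has four bullets under its primary endpoints heading:

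- "Number of respiratory exacerbations requiring antibiotic treatment"
- hospitalisations "due to respiratory exacerbations, using NHANES 2011 questionnaire for Hospitalisation and access to care HUQ.010"
- a nocturnal set: "Nocturnal oximetry and polygraphy outcomes: Basal SpO2 (%), Minimum SpO2 (%), Maximum SpO2 (%), Average SpO2 (%), Oxygen desaturation index (ODI", with snoring and end-tidal CO2 completing it
- "Rate of decline of pulmonary function"

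No bullet, and no measure within the nocturnal set, is placed first.

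Section 2 ranks these outcomes differently. Its primary objective is to explore whether treatment reduces respiratory-related complications, a term not defined as a variable or a composite. The antibiotic outcome appears under the secondary objectives, as an effect "on the number of courses of antibiotic prescribed compared to year before starting treatment". Hospitalisations, nocturnal oxygenation and ventilation, and decline in pulmonary function appear there too. The last is limited to children with neuromuscular disease who can do spirometry.

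Under "Primary endpoint analysis", section 6 assigns tests to each of the four outcome families. It states no significance level, sidedness, order of testing, multiplicity method or criterion for success.

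Section 1.2 nevertheless sets a directional claim: "Hypothesis: Nebulised Hypertonic Saline in children and young people with Neuromuscular disease or Cerebral Palsy decreases respiratory-related complications".

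**The concern.** A reader cannot tell which result answers the study question. Every outcome that is primary in section 3.1 belongs to a secondary objective in section 2, and the primary objective has no variable of its own. With ten unranked candidates and no decision rule, the hypothesis could be called supported on whichever variable reaches significance. The plan also cannot settle a mixed result, such as fewer antibiotic courses alongside a lower minimum SpO2.

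This matters more than usual because of the design. Section 3 describes a review of charts from December 2011 to May 2018, so much of the data predates the analysis. Naming the deciding endpoint in advance is then a main safeguard against choosing it after the results are seen.

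**Working it through.** **The plan's own figure.** There is none to reproduce. The documents give no significance level, power or multiplicity calculation, and the target of 40 per group is justified only by the pilot label.

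**Count of primary variables (section 3.1).** Antibiotic-treated exacerbations 1 + hospitalisations 1 + nocturnal measures 7 (basal, minimum, maximum and average SpO2, ODI, snoring, end-tidal CO2) + lung-function decline 1 = 10.

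**Section 3.1 against section 2.**

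| Outcome family | Section 3.1 | Section 2 |
|---|---|---|
| Antibiotic-treated exacerbations / antibiotic courses | primary endpoint | secondary objective |
| Respiratory hospitalisations | primary endpoint | secondary objective |
| Nocturnal oximetry and polygraphy | primary endpoint (7 variables) | secondary objective |
| Decline in pulmonary function | primary endpoint | secondary objective (neuromuscular spirometry subgroup) |

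The first row also differs in definition. Section 3.1 counts exacerbations, while sections 2 and 6 and the parent questionnaire count courses of antibiotics. The two differ whenever one exacerbation needs two courses.

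**Chance of a false positive.** Assumptions: each of the ten variables is tested once at two-sided 5%, and there is no true effect on any of them. The hypothesis is directional, so the relevant event is a significant result in the favourable direction, with probability 0.025 per test.

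- Favourable, independent: 1 − 0.975^10 = 1 − 0.776 = 22.4%
- Either direction, independent: 1 − 0.95^10 = 1 − 0.599 = 40.1%

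Independence is unlikely: four of the ten variables summarise SpO2 and a fifth counts desaturations. Normal test statistics were therefore simulated (400,000 draws), oriented so that positive is favourable, under two structures: all ten equally correlated, or only the seven nocturnal measures correlated.

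| Correlation | Favourable, all ten | Favourable, seven only | Either direction, all ten | Either direction, seven only |
|---|---|---|---|---|
| 0.3 | 17.8% | 20.1% | 35.0% | 37.5% |
| 0.5 | 14.3% | 18.0% | 28.6% | 33.8% |
| 0.7 | 10.6% | 15.5% | 21.2% | 29.5% |
| 0.9 | 6.4% | 12.7% | 12.8% | 24.1% |

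A single primary endpoint would give 2.5% in the favourable direction and 5% in either. These figures leave out the second test named for lung function and the Cox model on the primary endpoints, both of which would add tests.

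**Price of the alternatives.** Assume 40 analysable before/after pairs and 80% power. The detectable standardised effect is (z for alpha + z for power)/√n.

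- One primary at 5%: (1.960 + 0.842)/√40 = 0.44 SD
- All ten kept, Bonferroni at 0.05/10 = 0.005: (2.807 + 0.842)/√40 = 0.58 SD

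**The case against.** The strongest reply is that this is a pilot chart review whose primary objective is to explore. It states no power and no success criterion, so strict family-wise error control is not an obvious requirement. That stands, and it lightens the remedy. It does not remove the problem. Sections 1.1 and 1.2 state an aim to assess effectiveness and a directional hypothesis, the pilot label is used only to justify the sample size, and no feasibility objective is given. The conflict between sections 2 and 3.1 needs correcting whatever view one takes of multiplicity.

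It can also be said that section 2 is an umbrella objective followed by its components. That would explain the layout, but it still leaves no component, or combination of components, that decides the umbrella question.

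Section 6 names the nocturnal outcomes as a family and does not list seven tests. Seven is a reasonable inference, but an inference. Counted as four independent tests, the chance is 1 − 0.975^4 = 9.6% for a favourable result and 1 − 0.95^4 = 18.5% in either direction.

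Three stronger readings are tempting, and the documents do not support them:

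- **That the plan lets one significant result prove the hypothesis.** It contains no such rule. It is silent, and the risk comes from the silence.
- **That 40% is the size of the problem.** That figure needs independence and counts worsening as well as improvement, whereas the hypothesis concerns improvement only.
- **That the risk is 64%, from repeating ten tests in two diagnosis groups (1 − 0.95^20).** Section 6 plans no separate analysis by diagnosis, section 2 confines lung function to neuromuscular disease, and the groups of 40 are not defined as diagnosis groups.

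**Conclusion.** The concern holds in a limited form. The count of ten, the lack of a deciding endpoint or decision rule, and the mismatch between sections 2 and 3.1 can all be read directly from the protocol. At family level, all four primary outcomes are also secondary objectives.

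The size depends on assumptions that the documents do not supply: two-sided 5% per variable, one test for each of ten variables, and no true effect. On that footing the chance of at least one favourable false positive is about 22% under independence and about 6% to 20% for correlations from 0.9 down to 0.3. The either-direction range, about 13% to 40%, is secondary. This is a point that should be corrected before analysis. It does not show that the investigators intend to select a result.

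**What to change.** Before analysis:

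1. Designate one primary endpoint in section 3.1 and state that the hypothesis in section 1.2 is judged on it alone. Antibiotic-treated respiratory exacerbations in the 12 months after starting, against the 12 months before, is a reasonable candidate: it is listed first and is not limited to the spirometry subgroup. The documents do not rank it above hospitalisation, so the investigators should confirm and justify the choice.
2. Use one definition throughout, either exacerbations or antibiotic courses, in sections 2, 3.1 and 6.
3. Make that outcome the primary objective in section 2. Moving only the others would leave the contradiction in place, because section 2 now lists antibiotic courses as secondary.
4. Move the other nine variables to secondary in sections 2, 3.1 and 6. Report them as estimates with 95% confidence intervals and without confirmatory claims. Apply a Holm adjustment only if p-values are used to claim an effect.

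Cost: wording changes and no new data. Nine variables lose the primary label. Section 7.1 says that ethics approval has been obtained, so a protocol amendment may be needed.
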